### *Intervention and control groups*

#### Group A (Hand scanner instant feedback)

Participants will be informed about their hand scanner results of the first HW attempt to get individualized feedback about their hand wash performance. But no training video is provided.

#### Group B (Video training)

Participants will watch a training video about the 7 steps of hand washing after the first HW attempt, but they will not be informed about their hand scanner results.

#### Group C (Hand scanner + Video training)

Participants will be informed about their hand scanner results during the first HW attempt. They will also watch a training video about the 7 steps of hand washing.

#### Group D (Control group without intervention)

Participants will not be informed about the hand scanner results in the first HW attempt and no training videos will be provided.

### *Post-intervention assessment*

The participants will take the second HW attempt by putting fluorescent powder on both of their hands again and then perform hand wash with videos recorded. Digital images of hands will again be taken under UV light before and after hand wash. After washing hands, participants will scan fluorescent residual remained on their hands again in a hand scanner.

Participants will also be asked to fill in a questionnaire on knowledge and practice of hand hygiene as part of post-intervention assessment.

For the training purpose, after the completion of post-intervention measurements, the participants of the control group (Group D) will watch the training video and repeated hand washing and scanning for the third time if they agree. But the results of their third HW attempt will not be included into data analysis in this

Protocol  
Date 1 May 2023

study.

### **Randomization, allocation concealment, and blinding**

Participants will be randomly assigned to the intervention groups or control group through a process of randomization performed by a statistician who will not be involved in subject recruitment. The participants will be blinded. The RAs involved in subject recruitment and the IPC experts who judge the quality of hand hygiene will be blinded to the groupings. The RAs and student assistants involved in hand hygiene video recording at the study site will not be blinded because they will be giving instructions to the participants.

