## Methods

### *Study design*

This is a four-arm RCT.

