### *Subject recruitment*

We will recruit all year one nursing students from the Bachelor of Nursing and Bachelor of Mental Health Nursing program in School of Nursing (total number is approximately 280) during June to July 2023. The participants will subscribe a timeslot of training sessions (each session has 3 participants). All participants who attend the same session will be assigned to the same group by cluster randomization. A statistician will assign the groups in advance by a random number generator. The participants will not be informed about their group before arriving the study site (the Squina International Centre for Infection Control in PolyU).

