### *Pre-intervention assessment*

During the site visit, the participants will sign a consent form first and be asked to fill in a questionnaire on knowledge and practice of hand hygiene (attached in Appendix).

Participants will need to put fluorescent powder on both of their hands, and hold hands under ultraviolet (UV) light (wavelength: 365nm) to take digital image of hands. Participants will then perform hand washing using liquid soap without any instructions (1st HW attempt). The camera installed above the hand-wash basins will take videos of both hands (no face nor other parts of the body) during this procedure. After washing hands, participants will hold hands under UV light again to take digital image of hands, and will need to scan fluorescent powder remained on their hands in a hand scanner (The Semmelweis ScannerTM). The digital images of hands and the recorded hand washing videos will be used to train the AI algorithms for automatic image processing and assessments. Two IPC experts will judge the quality of hand hygiene in these images/videos, which will be adopted as ground truth in image processing. The percentage of fluorescent gel residual on hands shown in the hand scanner will be used as an objective assessment for efficacy of hand washing in individual participants.

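### Does the protocol name two different units of randomisation, so that 280 students could be wrongly analysed as independently randomised?

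*Protocol*

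**What the plan says.** The unit of allocation appears in the Protocol's Subject recruitment section. Students book their own slots: "The participants will subscribe a timeslot of training sessions (each session has 3 participants". The section continues: "All participants who attend the same session will be assigned to the same group by cluster randomization". On method it adds: "A statistician will assign the groups in advance by a random number generator". The pool is the year-one intake ("total number is approximately 280) during June to July 2023").

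Two other places describe the design without mentioning the session. Study design says only "This is a four-arm RCT". The section on randomization, allocation concealment and blinding says "Participants will be randomly assigned to the intervention groups or control group through a process of randomization performed by a statistician", and then covers who is and is not blinded.

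The main objective measure is taken on each student: the scanner residual "will be used as an objective assessment for efficacy of hand washing in individual participants" (Pre-intervention assessment). The Protocol gives no analysis model, intraclass correlation, power calculation or allocation ratio.

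**The concern.** The fact that defines the design, allocation by session, stands once, under recruitment. It is absent from the two sections where an analyst would look for it. Someone working from the randomisation section alone could take the trial as individually randomised and analyse about 280 independent students, when at most about 93 units are allocated.

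Some correlation within sessions is plausible. Students choose their slots, so classmates may book together, and those in one session share the visit and the staff who instruct them. If that correlation is positive and ignored, every comparison between arms has intervals that are too narrow and a type I error above the nominal level.

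A second worry concerns arm sizes. If the random number generator means an unrestricted list, the number of sessions per arm is left to chance.

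**Working it through.** **Is there a contradiction?** Set side by side, the two sections answer different questions. Subject recruitment says how allocation works: everyone in a session goes to the same group. The randomisation section says who performs it (a statistician outside recruitment) and who is blinded. It does not say that participants are randomised individually or independently. Students in a cluster trial are also randomly assigned to groups, through their cluster. Both sections give the task to a statistician, and nothing in one excludes the other. The design line does not exclude clusters either.

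**Is there a stated figure to reproduce?** No. The 280 is a count of available students, not a powered sample size, so no precision claim is overstated.

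**How large would the error be if sessions were ignored?**

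Inputs from the Protocol: N = 280 and session size m = 3. Assumptions: all students enrol, sessions are full, arms are equal, the test is two-sided at 5%, and the intraclass correlation (ICC) ranges from 0 to 0.20.

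- Sessions: 280 / 3 = 93.3. Per arm: 93.3 / 4 = 23.3 sessions, or 280 / 4 = 70 students.
- Design effect: DE = 1 + (m − 1) × ICC = 1 + 2 × ICC.
- Effective sample size: 280 / DE.
- Shortfall of the naive standard error: 1 − 1/√DE.
- True error of a nominal 5% test: 2 × [1 − Φ(1.96/√DE)].

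| Assumed ICC | DE | Effective N | Naive SE too small by | True type I error |
|---|---|---|---|---|
| 0 | 1.00 | 280 | 0% | 5.0% |
| 0.01 | 1.02 | 275 | 1.0% | 5.2% |
| 0.05 | 1.10 | 255 | 4.7% | 6.2% |
| 0.10 | 1.20 | 233 | 8.7% | 7.4% |
| 0.20 | 1.40 | 200 | 15.5% | 9.8% |

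Worked line for ICC 0.10: DE = 1 + 2 × 0.10 = 1.20; 280 / 1.20 = 233; 1.96 / √1.20 = 1.789; 2 × [1 − Φ(1.789)] = 0.074.

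**Arm sizes.** If 93 sessions were allocated to four equal arms with no restriction, simulation gives a mean gap of 9.9 sessions between the largest and smallest arms. The probability of a gap of 10 or more (30 students) is 0.50. The variance of a pairwise comparison would rise by a median of about 2% and a mean of 3.5% over equal arms. The Protocol does not say the list is unrestricted; a blocked list is also made with a random number generator.

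**The case for a change.** The strongest case for a change is that the unit of randomisation is a fact of design and belongs in the Protocol, not in the analysis plan. An analysis plan drafted only from the design line and the randomisation section would describe the wrong design. The individual-level outcome makes that slip easier, correlation within sessions is plausible, and the remedy would cost a few words.

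Much of this stands. The unit does belong in the Protocol, the randomisation section would read better if it named the session, and the direction of the error is right for any positive ICC. But the unit is in the Protocol, in the section that describes how students reach their group, and it is called cluster randomisation there. An analyst who reads this short document through will meet it.

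The inflated error needs a further step, an analysis of students as independent, which the Protocol nowhere plans. Whether to use a session random effect, cluster-robust standard errors or session means is a modelling choice commonly left to the analysis plan. The point on arm sizes rests on a scheme the Protocol does not state, and unequal arm sizes alone would cost a little precision without biasing a comparison.

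**Conclusion.** The concern does not hold as a contradiction. The Protocol states one unit of randomisation, the session of three. The sentence in the randomisation section is general wording that leaves the unit out. This is a gap in repetition that an analyst fills sensibly from Subject recruitment.

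The arithmetic on ignoring sessions is sound but conditional. The true error would lie between 5.0% and 9.8% for an ICC between 0 and 0.20, given full sessions and an analysis that disregards them. The upper figure needs an ICC of 0.20, which nothing in the Protocol supports or rules out. Since 280 is a recruitment pool and participation is voluntary, 93 sessions is about the most the trial could have, and no stated sample size is shown to be wrong. The arm-size point falls away because an unrestricted list is not specified.

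The conclusion assumes that the analysis will account for sessions, as the stated cluster randomisation implies. An analysis plan that treated the students as independent would itself be a finding, but none is at hand.

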**NCT05872581**

**Date: 1 May 2023**

## Background

The ongoing COVID-19 pandemic has posed serious threats to public health worldwide. Although children have mild symptoms, they have been found to more likely transmit the virus within the household than the other age groups. The importance of hand hygiene cannot be underestimated in both healthcare and community settings (Allegranzi et al., 2011; Mathur, 2011). The promotion of hand hygiene is the best practices in preventing health care-associated infection (WHO, 2009). It has been estimated that hand hygiene could reduce over 500 000 attributable deaths per year. It was found that the annual economic impact of health care-associated infection in the US was approximately US\$6.5 billion in 2004 (WHO, 2009) and every US\$1 spent on hand hygiene promotion could result in a US\$23.7 benefit (Chen et al., 2011). Education plays a key role in setting a good practice base in hand hygiene.

The traditional training methods for nursing students include in-class lecture and practical, but students seldom receive individualized instructions and feedbacks due to limited manpower and facilities. Hence, there is an urgent need of designing an automated and individualized education program. This study aims to design and test a multicomponent education program of hand hygiene in nursing students. Specifically, this program has two components: 1) training videos according to the WHO guidelines on hand hygiene in health care (<https://polyu.ap.panopto.com/Panopto/Pages/Viewer.aspx?id=f3973cee-bcfb-48fd-a306-b6893dacaabd>); 2) a hand scanner used for students to immediately visualize the missing spots of hand hygiene.

This study has the following specific objectives:

- 1) conduct a randomized controlled trial (RCT) to test the effectiveness of this program on knowledge and practice of hand hygiene in nursing students;
- 2) evaluate the effects of each component and collect feedbacks from participants.

If demonstrated effective, this program can be integrated into the curriculum of nursing students as an e-learning approach. In future, this system can also be used at point-of-care for real-time monitoring and audit of healthcare workers in other healthcare settings.

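### The unqualified claim of participant blinding fails once the arms diverge, and concealment of the group through baseline is feasible but not secured

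*Protocol*

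**What the plan says.** Three parts of the protocol bear on what participants know, and when.

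- **Blinding.** The section *Randomization, allocation concealment, and blinding* says "The participants will be blinded". It then says that recruiting research assistants (RAs) and the infection-control (IPC) experts who judge hand hygiene are blinded to the groupings. On-site RAs and student assistants who handle video recording are not blinded, because they instruct the participants. No time is given from which they know the group.
- **Allocation.** Under *Subject recruitment*, students book sessions of three and everyone in a session gets the same group. "A statistician will assign the groups in advance by a random number generator". On withholding, it says "The participants will not be informed about their group before arriving the study site".
- **Procedures.** *Pre-intervention assessment* begins "During the site visit, the participants will sign a consent form first and be asked to fill in a questionnaire". Then: "Participants will then perform hand washing using liquid soap without any instructions". Afterwards participants "will need to scan fluorescent powder remained on their hands in a hand scanner". Only then do the arms differ. For Group A: "Participants will be informed about their hand scanner results of the first HW attempt to get individualized feedback about their hand wash performance". Group B watches a video without being told the scan result, Group C gets both, and Group D gets neither. The second wash, scan and questionnaire follow under *Post-intervention assessment*.

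**The concern.** The arms are defined by two things that participants experience directly: being told a scan result and watching a video. *Background* describes the scanner component as "a hand scanner used for students to immediately visualize the missing spots of hand hygiene", so visibility is the point of the intervention. A general statement that participants are blinded does not fit this design.

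Two things are at stake. First, the trial could be reported as participant-blinded for outcomes where it is not. The second wash depends on the participant's effort and the questionnaire is self-completed, so knowledge of the training received can act on both. Second, the period before the arms diverge can be protected, but the text does not protect it clearly. If the group became known early, it could affect willingness to consent, effort in the baseline wash, or the cues staff give during it.

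**Working it through.** No formula applies and the plan gives no figure to reproduce. The check follows the visit in order and compares what participants and staff may know with what is measured next.

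1. **Before arrival.** *Subject recruitment* explicitly withholds the group from participants. Slots are therefore booked without knowledge of the group.
2. **Arrival to the end of the first scan.** *Pre-intervention assessment* gives one procedure for everyone: consent, questionnaire, imaging, first wash and scan. Nothing in it is specific to a group, so neither participants nor staff need the group during this period. The only explicit time point for withholding it, arrival, has already passed. What remains is the general blinding sentence, for participants only.
3. **Staff in the same period.** The group already exists, because it is assigned in advance by session. The staff named as unblinded are those at the video recording, and the first wash is recorded. The reason given for unblinding them is that they give instructions, but the first wash is done without any. The stated reason therefore does not apply at baseline, yet the exemption has no start time and covers baseline as written. The protocol does not say who takes consent on site.
4. **After the first scan.** The arms become visibly different:

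| Group | Told scan result | Watches video | Visible component |
|---|---|---|---|
| A | yes | no | yes |
| B | no | yes | yes |
| C | yes | yes | yes |
| D | no | no | no |

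   Three of four arms receive a visible component. No sham feedback or attention-control video is described.
5. **Outcomes.** Both post-intervention assessments, the second wash with its scan and the questionnaire, come after step 4. Group D sees the video only once these are complete.

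The blinding sentence can thus be true of steps 1 and 2. From step 4 it cannot be true of the intervention received in Groups A, B and C.

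**The case against.** The strongest reply is that the sentence means blinded to group, not to the experience of training. The next sentence in that section speaks of blinding to the groupings, and participants can be read in parallel. The design gives this some support. Everyone in a session has the same group, so nobody sees a contrasting treatment there, and Group D's video is delayed until after the measurements. A student who watches a video need not know that other arms exist. This reading is possible, and it is why the point stops at saying that participants could at most be unaware of the other arms. But the protocol nowhere says that participants are not told of the other arms. If that is the meaning, it has to be stated.

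It is also fair to say that several safeguards already exist. The scanner reading is objective, the IPC experts and recruiting RAs are blinded, and unblinding to the training received is inherent in this kind of intervention. All of that stands. The defect is the claim of blinding and the avoidable gap before the arms diverge, not the choice of intervention.

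Two stronger readings are tempting and are not supported:

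- A reader might infer that participants are told their group on arrival. The protocol says only that they are not told before then. No early disclosure is planned, and the general blinding sentence can be read as covering the baseline period.
- A reader might infer that participants will work out their group from the information sheet. The sheet is not shown, so nothing can be concluded from it.

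**Conclusion.** The point holds in two parts. The participant-blinding sentence is wrong as an unqualified statement: in 3 of 4 arms participants know which training they received before both post-intervention assessments. Concealment of the group through consent and baseline is feasible, because the procedure is common to all arms, but it is not secured. Groups exist in advance, and on-site staff are unblinded with no stated start.

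The documents allow no estimate of the size of any bias, and none is claimed. The conclusion assumes that no sham or masking exists beyond what the protocol describes. It does not undermine the arms, the session randomization or the assessments. The text and the handling of the allocation list should be corrected.

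**What to change.** 1. Keep each session's pre-generated group concealed from participants and on-site staff, by sealed envelope or locked electronic list. Open it only when every participant in the session has consented and completed the baseline questionnaire, first wash and scan. State this time point in both *Subject recruitment* and *Randomization, allocation concealment, and blinding*.
2. Replace the participant sentence with wording such as: *Participants are unaware of their group until their session's baseline is complete and are not blinded to the intervention they then receive.* Add, only if true, that they are not told of the other groups until the post-intervention assessment is complete. Do not report the trial as participant-blinded for the post-intervention outcomes.
3. Amend the last sentence of the blinding section so that on-site staff are unblinded only from the end of the session's baseline. Without this, change 1 would contradict it.

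**Cost.** With approximately 280 students in sessions of three, 280/3 = 93.3, so about 93 envelopes or one locked list, plus a few sentences of protocol text. The small downside is that site staff must be ready to run any arm at short notice. Arms, randomization unit and assessments are unchanged.

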### **Ethical consideration**

The effect of exposure to UV-A light is similar to outdoor exposure to sunlight. It is anticipated that the study will not pose any physical or psychological harm to the participants. The contact details of either the ethical or the research in-charge personnel are clearly written in the information sheet.

Explanation of the study will be given to participants who are interested in participating in the study. Participants will also be given the opportunity to ask our project personnel questions. Furthermore, the information sheet including the purpose of the study, confidentiality of the data, and rights of the participants, will also be provided to the participants. The contact details of either the ethical or the research in-charge personnel are clearly written in the information sheet. If they agree to participate in the study, they are required to sign the consent form. Their participation is on a voluntary basis, they have the right to withdraw from the study at any time if they want to without consequence.

All the collected data will be kept confidentially, and only the research personnel can access and handle the data. No personal information of the participants will be collected except the student ID number.

### **Confidentiality and Security**

Data collection will be anonymous, only analysed for specified purposes and on the basis of the consent or other legitimate basis laid down by law. No personal information will be linked to image/video data. All the image/video data will be deleted one year after the project is completed. The Project will not involve any activities or results raising security issues.

Appendix

**Survey on knowledge and practice of Hand Hygiene in Nursing Students**

**Part I: Demographic**

1. Student ID: \_\_\_\_\_
2. Age: \_\_\_\_\_ yrs
3. Gender:      Female      Male
4. Programme:      BSN      Mental Health Nursing

**Part II: Hand hygiene**

5. Have you ever received formal training in hand hygiene?

Yes      No

If your answer is yes; when did you receive the training (give the latest year)?

Answer: \_\_\_\_\_ (yyyy)

6. How many steps are required for healthcare workers to perform hand hygiene (please give a number) ?

Answer: \_\_\_\_\_

7. How many types of hand hygiene are there (please give a number)?

Answer: \_\_\_\_\_

8. How long is the minimal duration of hand washing?

Answer: \_\_\_\_\_ seconds

- 9: Which of the following sequence is correct for hand hygiene? (MC Question)

A	Ans: B	C
Finger webs	Finger webs	Thumbs
Finger tips	Back of fingers	Finger tips
Back of fingers	Thumbs	Finger webs

Protocol

Date 1 May 2023

Thumbs	Finger tips	Back of fingers
--------	-------------	-----------------

10. Which of the following is one of hand hygiene steps EXCEPT?

- Rub palms
- Rub fingernails
- Rub wrists
- Fingers interlocked

11. Do you agree or disagree with the following statement:

Hand hygiene is part of infection prevention and control in healthcare settings.

- Strongly agree
- Agree
- Neither agree nor disagree
- Disagree
- Strongly disagree

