**Additional questions for post evaluation**

12. What are the 7-steps of hand washing? (MC Questions)

	A	B	C	Answers
Step 1	Finger tips	Palms	Between fingers	Palms
Step 2	Back of hands	Back of fingers	Palms	Back of hands
Step 3	Thumbs	Finger tips	Between fingers	Between fingers
Step 4	Palms	Between fingers	Back of hands	Back of fingers
Step 5	Finger tips	Thumbs	Back of fingers	Thumbs
Step 6	Back of fingers	Finger tips	Wrists	Finger tips
Step 7	Wrists	Thumbs	Back of hands	Wrists

13. What is the sequence for hand hygiene?

Steps		Drag Answer Here:
Finger tips	Step 1	
Back of hands	Step 2	
Thumbs	Step 3	
Palms	Step 4	

Protocol

Date 1 May 2023

Finger tips	Step 5	
Back of fingers	Step 6	
Wrists	Step 7

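### Knowledge item 10 has a contradictory stem and options that do not match the trial's own seven-step key, so it is ambiguous, though it can still be scored (minor)

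*Protocol*

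**What the plan says.** The first objective in the Protocol's Background section is to "test the effectiveness of this program on knowledge and practice of hand hygiene in nursing students". The sections on pre-intervention and post-intervention assessment each have participants fill in a questionnaire on knowledge and practice, and the Appendix prints it.

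Item 10, in Part II of the Appendix, has the stem "Which of the following is one of hand hygiene steps EXCEPT". Its four options are palms, fingernails ("Rub fingernails"), wrists and "Fingers interlocked".

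The trial's own list of steps comes later, under the heading for additional post-evaluation questions. Item 12 asks "What are the 7-steps of hand washing? (MC Questions") and carries an answer column. Read downwards, that column gives palms, back of hands, between fingers, back of fingers, thumbs, finger tips and wrists. The row for the sixth step, for example, reads "Step 6 Back of fingers Finger tips Wrists Finger tips", where the last entry is the keyed answer.

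Only items 12 and 13 stand under the post-evaluation heading, so item 10 appears to be asked both before and after the intervention.

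**The concern.** The stem gives two opposite instructions. A student who follows its first half can properly choose palms or wrists. A student who follows the last word must find the one option that is not a step, and the options do not make that clear-cut, because two of the four use names that the key does not use.

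The item tests the content that the training video in Groups B and C is meant to teach, so it should respond to training. If some students misread the stem, or hesitate to exclude fingernails because they have learned that finger tips are a step, the item responds less than it should. The knowledge comparison then loses some sensitivity. An analysis plan could add a scoring rule or drop the item, but it cannot change the words that participants read.

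**Working it through.** **Step 1. Options against the key.** The key is the answer column of item 12.

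| Item 10 option | Keyed label | Match |
|---|---|---|
| Palms | Palms (step 1) | Same label |
| Wrists | Wrists (step 7) | Same label |
| Fingers interlocked | None; describes between fingers (step 3) or back of fingers (step 4) | By meaning only |
| Fingernails | None; nearest is finger tips (step 6) | Arguable overlap |

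The number of exceptions depends on the reading:

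- Labels only: two (fingernails, fingers interlocked).
- Interlocked fingers matched by meaning, fingernails by label: one (fingernails). This is the most natural reading.
- Both matched by meaning: none.

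The form's naming does not settle the matter. What seems to be one and the same step is called finger webs in item 9, interlocked fingers in item 10 and between fingers in item 12.

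**Step 2. Possible size.** The Protocol gives no scoring rule and no expected proportions correct, so this is an illustration on assumptions: a score that counts correct answers on items 6 to 10 (the five factual items that appear to be on both forms), independent items, and 50% correct without training against 80% with it.

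Standardised effect = difference in mean score / square root of the average of the two group variances. One sound item contributes a difference of 0.80 − 0.50 = 0.30 and an average variance of (0.50 × 0.50 + 0.80 × 0.20)/2 = (0.25 + 0.16)/2 = 0.205.

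- Five sound items: 5 × 0.30 = 1.50; variance 5 × 0.205 = 1.025; 1.50/√1.025 = 1.48.
- Four sound items, item 10 a coin flip in both groups: 4 × 0.30 = 1.20; variance 0.82 + 0.25 = 1.07; 1.20/√1.07 = 1.16. Loss 1 − 1.16/1.48 = about 22%.
- Item 10 keeps half its signal (50% to 65%): 1.20 + 0.15 = 1.35; variance 0.82 + (0.25 + 0.2275)/2 = 1.059; 1.35/√1.059 = 1.31. Loss about 11%.
- Item 10 left out: 1.20/√0.82 = 1.33. Loss about 11%.

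So the loss runs from none (item fully sound) to about 22% (item pure noise). If the item keeps about half its signal, keeping it and dropping it come to nearly the same.

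**Step 3. A longer score.** If items 12 and 13 also count in a post-intervention comparison, as one point each, the sound score gives 7 × 0.30 = 2.10 and 2.10/√1.435 = 1.75. With item 10 as noise it gives 1.80/√(1.23 + 0.25) = 1.80/√1.48 = 1.48. The upper limit of the loss falls to about 16%.

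**The case against.** The strongest reply is that the item works despite its grammar. The capitalised last word of the stem shows that the non-step is wanted, and a single-answer item makes sense only on that reading. By elimination, palms and wrists are keyed, interlocked fingers describe a keyed step, and fingernails are named nowhere in the key, which leaves one best answer. This stands. A reader might infer that the item cannot be scored as right or wrong, or that a student who knows the seven steps would be marked wrong. The documents support neither: the first requires fingernails and finger tips to be treated as the same thing, and the second requires a scoring key that they do not contain.

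A reader might also count it as a defect that no answer is printed beside item 10, when items 9 and 12 show theirs. It is not one. Items 6, 7, 8 and 13 show no answer either, and a scoring key may sit in a document that is not at hand.

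It is fair to add that all four groups answer the same item, so nothing here shows a bias between them, and that the scanner residual, which the Protocol uses as its objective assessment of hand washing, is untouched.

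What the reply does not remove is the wording. The stem still contradicts itself, and the intended answer still overlaps in meaning with a keyed step.

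**Conclusion.** The point holds as a minor one. Item 10 has a contradictory stem, and two of its options do not use the labels of the trial's own key. It can be scored, with fingernails as the likeliest intended exception, but it is ambiguous and so adds some noise to a knowledge outcome named in the first objective.

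The size is a range: from no loss to about 22% of the standardised effect. It rests on an assumed five-item score, independent items and 50% versus 80% correct. A reader might take 22% as the expected loss. It is the limit for an item with no training signal at all, on a score that the Protocol never defines. An item with a discernible best answer should keep some of its signal, and a longer score would dilute the effect further. The trial's conclusions on hand-washing performance do not depend on this item.

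**What to change.** Before the first session:

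- Reword the stem as a plain negative, for example: *Which of the following is NOT one of the 7 hand-washing steps?*
- Name the true steps with the item 12 labels, so that interlocked fingers becomes between fingers or back of fingers, whichever is meant.
- Replace the fingernail option with one that overlaps none of the seven keyed steps.

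The same text should go on the pre- and post-intervention forms so that the two remain comparable.

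If the form has already been used, keep the item as asked and report the knowledge result with and without it.

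The cost is one edited questionnaire item, or one additional line in the results.
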